**Table 5. Confusion matrix for Alcohol Domain**

Predicted risk levels defined by WHO ASSIST		TAPS Tool observation				
		0	1	2	3	4
Low risk level	XX (XX.XX%)	XX (XX.XX%)	XX (XX.XX%)	XX (XX.XX%)	XX (XX.XX%)	XX (XX.XX%)
High/moderate risk level	XX (XX.XX%)	XX (XX.XX%)	XX (XX.XX%)	XX (XX.XX%)	XX (XX.XX%)	XX (XX.XX%)

**Exploratory Statistical Aim 2: To assess the association between the NS metric and other measurements of opioid misuse.**

In this exploratory aim, we will assess the relationship between the NS metric with the established risk levels of low, moderate and high risk and 1) ordinal prescription and heroin use scores from the TAPS Tool (prescribed medication and heroin domains), 2) a positive misuse indication from (POMI), and 3) overdose frequency history.

Risk levels will be defined as follow:

- TAPS Tool prescribed medication domain:
  - High risk  $\geq 2$ ;
  - Low risk  $< 2$ .

- POMI:
  - High risk  $\geq 2$ ;
  - Low risk  $< 2$ .
- Overdose Frequency History - OESWD domain:
  - Any Overdose  $> 0$ ;
  - No Overdose = 0.

We will likewise employ the above described statistical analyses for Exploratory Aim 1 and assess the association and agreement level between NS metric and the TAPS Tool, POMI, and Overdose Frequency History with the:

- Confusion table;
- AUC of ROC analysis;
- Spearman Correlation Coefficient;
- Goodman and Kruskal's Gamma;
- Kendall rank correlation coefficient;
- Ordinal Logit Regression.

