### **2.2.3 TAPS**

The TAPS Tool consists of a 5-item screening for tobacco use, unhealthy alcohol use, prescription medication misuse, and illicit substance use. Positive reports on the screener result in respondents subsequently being asked 9 additional substance specific items. Scoring on the TAPS Tool involves summing respondents' answers to the substance specific questions, resulting in a 0-3 ordinal score for each drug (0=No use in the past 3 months; 1= problem use; 2= higher risk). The TAPS Tool has demonstrated concurrent validity. This measure will be captured in order to provide additional information regarding its psychometric properties compared to the WHO ASSIST.

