### **Exploratory Statistical Aim 1: To validate TAPS tool using WHO ASSIST as gold standard.**

The TAPS tool is rapidly becoming recognized as a high quality substance use screener for outpatient health care settings. Given the somewhat limited opioid using sample in the main outcomes study ( $\leq 5\%$  for prescription opioids;  $< 4\%$  for heroin\*), the current study offers an important opportunity to further validate this instrument in a novel outpatient setting, community pharmacy, among a large opioid using population.

The performance of TAPS Tool will be evaluated relative to WHO ASSIST. We plan to compare subjects' responses to each substance of TAPS Tool with their responses to the corresponding domains of WHO ASSIST. The TAPS tool has four domains, and WHO ASSIST has 9 domains. Domains on the ASSIST will be combined with those of the TAPS Tool, see **Table 4** for details:

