**Table 4: combinations of substances for WHO ASSIST**

ASSIST (past 3 months)	TAPS 1 (past 12 months)			
	Tobacco	Alcohol	Illicit Drug	Prescribed Medication
Tobacco products (cigarettes, chewing tobacco, cigars, etc.)	X			
Alcoholic beverages (beer, wine, liquor, etc.)		X		
Cannabis (marijuana, pot, weed, hash, etc.)			X	
Cocaine (coke, crack, etc.)			X	
Amphetamine type stimulants (speed, diet pills, ecstasy, methamphetamine, crystal-meth, etc.)			X	X
Inhalants (nitrous, glue, poppers, etc.)			X	
Sedatives or sleeping pills (Valium, Rohypnol, Ativan, Xanax, Klonopin, GHB, etc.)				X
Hallucinogens (LSD, acid, mushrooms, PCP, Special K, etc.)			X	
Opioids (heroin, morphine, methadone, codeine, buprenorphine, suboxone, Oxycontin, Percocet, Vicodin, etc.)			X	X
Other (K2, Spice, Synthetic spice, Synthetic marijuana)			X	

The level of agreement between TAPS tool with the established risk levels of low, moderate and high on the WHO ASSIST will be evaluated with similar methods as described in Aim 2: ROC analysis will be used to examine concordance between each domain of the TAPS Tool and the corresponding clustered domain of WHO ASSIST. Risk levels of the WHO ASSIST for each clustered domain are defined as follow:

- WHO ASSIST Tobacco Domain:
  - Moderate and High risk  $>3$
  - Low risk  $\leq 3$
- WHO ASSIST Alcohol Domain:
  - Moderate and High risk  $>10$
  - Low risk  $\leq 10$

- WHO ASSIST Illicit Drug Domain:
  - Moderate and High risk  $>3$
  - Low risk  $\leq 3$
- WHO ASSIST Prescribed Medication Domain:
  - Moderate and High risk  $>3$
  - Low risk  $\leq 3$ .

For each of these binary risk categories, Area under the ROC curve (AUC) values will be used to determine the overall discriminating ability of TAPS tool on each of the 4 domains.

The confusion table will be provided (see **Table 5 example of alcohol domain Confusion Table**) and the following statistical measurements of agreement, all with their respective 95% confidence intervals will be provided: Spearman correlation coefficient, Goodman and Kruskal's Gamma, and Kendall rank correlation coefficient. A logistic regression model will be built to estimate the magnitude of association between the metrics, while controlling for other relevant risk factors.

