Results for Exploratory Aim 1	Table 5.1	CP	TAPS Tool ROC curve for discriminating high risk vs low risk groups defined by WHO ASSIST, by domains (Tobacco, Alcohol, Illicit Drug, Prescribed Medication)
	Table 5.2	CP	TAPS Tool ROC curve for discriminating high risk vs low risk groups defined by WHO ASSIST, by domains (Tobacco, Alcohol, Illicit Drug, Prescribed Medication), by gender
	Table 5.3	CP	Summary of AUC of ROC curve for each domain
	Table 5.4	CP	Summary of AUC of ROC curve for each domain by gender
	Table 5.5	CP	Confusion Table for TAP Tool vs WHO ASSIST, for each domain
	Table 5.6	CP	Confusion Table for TAP Tool vs WHO ASSIST, for each domain, by gender
	Table 5.7	CP	Summary of Kappa Coefficient and Correlation Analysis Results, WHO ASSIST vs TAP Tools for each domain
	Table 5.8	CP	Summary of Kappa Coefficient and Correlation Analysis Results, WHO ASSIST vs TAP Tools for each domain, by gender
	Table 5.9	CP	Summary of ordinal logit regression results for each domain
	Table 5.10	CP	Summary of ordinal logit regression results for

Section	Table/Figure #	Analysis Population	Title
Results for Exploratory Aim 2 – explore association between NS metric vs TAP Tools			each domain, by gender
	Table 6.1.1	CP	Confusion Table for NS metric with established cut-off threshold vs TAPS Prescribed Medication Domain
	Table 6.1.2	CP	Confusion Table for NS metric with established cut-off threshold vs TAPS Prescribed Medication Domain, by gender
	Figure 6.1.3	CP	NS metric ROC curve for discriminating high risk vs low risk opioid misuse patients (defined by TAPS)
	Figure 6.1.4	CP	NS metric ROC curve for discriminating high risk vs low risk opioid misuse patients (defined by TAPS), by gender
	Table 6.1.5	CP	Summary of AUC of ROC curve, for NS metric vs TAPS
	Table 6.1.6	CP	Summary of AUC of ROC curve, for NS metric vs TAPS by gender
	Table 6.1.7	CP	Summary of Kappa Coefficient and Correlation Analysis Results, NS metric vs TAP Tools
	Table 6.1.8	CP	Summary of Kappa Coefficient and Correlation Analysis Results, NS metric vs TAP Tools, by gender
	Table 6.1.9	CP	Summary of ordinal logit regression results, NS metric vs TAP Tools
Results for Exploratory Aim 2 – explore association between NS metric vs POMI Tools	Table 6.2.1	CP	Confusion Table for NS metric with established cut-off threshold vs POMI
	Table 6.2.2	CP	Confusion Table for NS metric with established cut-off threshold vs POMI, by gender

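### Exploratory Aim 2 labels a TAPS result as opioid misuse, but its only TAPS risk level is for a domain that in SAP Table 4 also takes sedatives and stimulants, and heroin is named without a cut-off

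*SAP*

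**What the plan says.** The aim is titled "To assess the association between the NS metric and other measurements of opioid misuse". Three comparators follow: TAPS, the Prescription Opioid Misuse Index (POMI) and overdose history. For TAPS the aim promises "ordinal prescription and heroin use scores from the TAPS Tool (prescribed medication and heroin domains"). In the list of risk levels the only TAPS entry is "TAPS Tool prescribed medication domain", split at 2. There is no entry for heroin.

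In SAP Appendix 1, shells 6.1.1 and 6.1.2 (confusion tables) name the prescribed medication domain. Figures 6.1.3 and 6.1.4 carry the label "NS metric ROC curve for discriminating high risk vs low risk opioid misuse patients (defined by TAPS"). The remaining TAPS shells, up to 6.1.9, refer to TAPS without naming a score.

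Elsewhere, Exploratory Statistical Aim 1 states: "The TAPS tool has four domains, and WHO ASSIST has 9 domains". Table 4 names the four as tobacco, alcohol, illicit drug and prescribed medication. SAP 2.2.3 describes TAPS scoring as "resulting in a 0-3 ordinal score for each drug", with 2 meaning higher risk. SAP Table 1 lists TAPS prescription-opioid items and TAPS heroin items among the opioid severity measures.

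**The concern.** The aim and the figure labels concern opioids, while the one TAPS variable with a risk level carries the name of a domain that spans several drug classes. If the analyst follows the text as it stands, the AUC and confusion table reported for opioid misuse will rest on a case group that may include people with no opioid misuse. A reader of the results could not tell how much of the association concerns opioids. Heroin use, which the aim promises to cover, has no defined route into those binary analyses. The gender-comparison shell for NS associations (the second Table 7.3) would inherit both problems.

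**Working it through.** The plan states no figure on this point, so there is none to reproduce. The check sets the passages side by side.

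1. **Construct.** Opioid misuse, from the title of Exploratory Aim 2 and the labels of Figures 6.1.3 and 6.1.4.

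2. **Variable.** The prescribed medication domain at 2 or more, from the risk-level list and shells 6.1.1 and 6.1.2.

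3. **What that name covers in the SAP.** Three rows of Table 4 are marked under Prescribed Medication:
   - "Sedatives or sleeping pills (Valium, Rohypnol, Ativan, Xanax, Klonopin, GHB, etc".), under that column only;
   - "Amphetamine type stimulants (speed, diet pills, ecstasy, methamphetamine, crystal-meth, etc".), there and under Illicit Drug;
   - opioids, there and under Illicit Drug. This row lists heroin among its examples.

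   Shells 5.1 and 5.2 use the same four domain names.

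4. **Who becomes a case.** Take a patient who scores 2 on one drug class and 0 on the others. The text allows two readings of the variable:

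| Patient | Whole-domain reading (Table 4) | Prescription-opioid score only |
|---|---|---|
| Prescription opioid | case | case |
| Sedative only | case | non-case |
| Stimulant only | can be a case | non-case |
| Heroin only | not settled | non-case; heroin score has no level |

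   The two readings disagree for sedatives and stimulants. Neither gives heroin a defined place. On the whole-domain reading, Table 4 puts the opioid row, heroin included, under both columns, whereas SAP Table 1 groups the TAPS heroin items with illicit drugs.

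5. **Combining scores.** TAPS is scored per drug, and the SAP does not say how several drug scores make one domain value. Suppose a patient scores 1 for a sedative and 1 for a stimulant. A sum gives 1 + 1 = 2, which is high risk. A maximum gives 1, which is low risk.

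6. **Direction of the effect.** Protocol 7.2.1 builds the first two NS digits from five components with weights 3 (morphine equivalents), 2 (overlapping days) and 1 each for lorazepam equivalents, prescribers and pharmacies. The total is 3 + 2 + 1 + 1 + 1 = 8, so lorazepam equivalents carry 1/8 = 12.5% of the weight. Dispensed sedatives therefore raise NS directly, and sedative-only cases could strengthen the NS-TAPS association without any opioid misuse. No component measures the quantity of stimulants dispensed, so stimulant-only cases would more likely weaken it. The net sign depends on the mix of cases, which the documents do not give.

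**The case against.** The strongest reply is that the aim may already intend the opioid-specific scores. Table 4 was written for Exploratory Aim 1, to map ASSIST substances onto TAPS 1 columns covering the past 12 months, and it does not define a variable for Aim 2. The aim mentions a heroin domain, which Table 4 lacks, so it is not simply using that scheme. A cut at 2 fits the per-drug score in SAP 2.2.3, and SAP Table 1 pairs prescription-opioid items with heroin items much as the aim does. This stands as a possible reading. It does not remove the problem: the text uses the SAP's own name for the multi-class column, does not say which drug score is meant, and still gives heroin no level.

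Four stronger readings are tempting, and the documents do not support them:

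- *Heroin is left out of the aim.* It is named there, and Spearman, Gamma and Kendall statistics can use an ordinal heroin score without a cut-off. What is missing is a level and a named shell.
- *A heroin-only user is certainly a non-case.* The opioid row of Table 4 includes heroin and is marked under Prescribed Medication, so this is not settled.
- *The TAPS result does not measure opioid misuse.* Prescription opioids are in the domain. The comparator is non-specific, not unrelated.
- *The distortion of the AUC can be put in numbers.* That needs the share of sedative-only and stimulant-only cases and the AUC in each case type, and the documents give neither. Fixing the true AUC at 0.70 would place results on both sides of the SAP's poor/fair boundary by construction. Changing the case definition also moves those patients into the comparison group, so a simple mixture of AUCs with common negatives would not describe the change.

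**Conclusion.** The point holds as one of specification. Followed literally, the plan yields a non-specific TAPS comparator reported as opioid misuse, and it leaves the binary handling of heroin undefined. The literal reading assumes that the domain named in Exploratory Aim 2 is the column of the same name in Table 4. If the per-drug prescription-opioid score was meant, the remaining fault is that the SAP does not say so and gives heroin no level. The direction of any distortion is unknown and its size cannot be derived from the documents.

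The point is minor. TAPS is one of three comparators in an exploratory aim. POMI asks about opioid medications specifically (Protocol 7.3.1) and is unaffected, as is the primary analysis of NS against the ASSIST opioid domain.

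**What to change.** In SAP 3.5, Exploratory Statistical Aim 2, and in shells 6.1.1 to 6.1.9, replace the prescribed medication domain with the per-drug TAPS prescription-opioid and heroin scores. Apply the existing level of 2 or more to each, and define TAPS opioid misuse as either. If the whole domain is also kept, state how the drug scores are combined and label it as prescription medication misuse, any class.

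The items are already collected and scored per drug, so the cost is SAP wording and shell labels. Dropping sedative-only and stimulant-only cases is likely to leave fewer positives and somewhat wider intervals. Heroin alone may be too sparse for a separate analysis, in which case it should enter only through the combined indicator.

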### **Exploratory Statistical Aim 3: To validate definition of NS metric.**

In this section, we will validate the definition of NS metric and test if the third digit of NS metric (number of opioid prescription) is informative. We will examine an alternative definition of NS metric, named as NS metric v2, which consists of only the first two numbers of original NS metric, which ranges 00-99. Descriptive analyses will be conducted and correlation between NS metric and NS metric v2 will be examined with Spearman Correlation Coefficients. We will repeat the planned training/validation analyses in the primary analysis and compare the discriminative ability of NS metric v2 vs. NS metric. We expect the predictive power of NS metric v2 is lower than that of NS metric, which implies the 3rd digit in NS metric original definition is predictive. We will also repeat the training/validation analysis within each subgroup of patients with same numbers of opioid prescriptions. The overall discriminate ability for NS metric 2, described by average misclassification rate across subgroups, will be compared with primary analyses results. It is expected that the prediction accuracy is comparable, which implies the “opioid prescription number” information is well represented by the third digit of original NS metric definition.

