7.2.1 NS metric

The NS metric is a continuous indicator on a 000-999 scale, with the last digit representing number of active opioid prescriptions (those with ≥ 9 prescriptions coded as 9) and the first two numbers representing a composite risk score. Higher scores indicate increased risk for adverse opioid-related outcomes (e.g., overdose). The first two digits of the score are based on deterministic calculations^{3,4} and use well-known indicators associated with opioid-related adverse events.⁴⁹⁻⁵² These calculations are produced through the following steps:

- 1) For a given patient, raw indicators of five risk factors are extracted from PDMP data: (a) morphine milligram equivalents (MME) dispensed, (b) lorazepam milligram equivalents (LME) dispensed, (c) overlapping prescription days, (d) number of prescribers, and (e) numbers of pharmacies.
- 2) Each raw indicator is converted to a scaled value between 0 and 99 (based on percentiles from a large PDMP reference population), for four time periods: (a) past 2 months, (b) past 6 months, (c) past 12 months, and (d) past 24 months. Therefore, each patient is assigned 20 scaled percentile values. These scaled values weigh the contribution of recent values more heavily than values further in the past; for example, having 6 unique prescribers over the past 2 months has a greater scaled percentile score (i.e., 85) than having 6 unique prescribers over the past 2 years (i.e., 30).
- 3) Scaled values for each of the five indicators are averaged across their four respective time periods.
- 4) A weighted sum of the five averaged values is calculated: MME is given a weight of 3; overlapping medication days is given a weight of 2; and LME, number of prescribers, number of pharmacies are each given a weight of 1. This sum is divided by 8 to produce a weighted average, yielding a two-digit composite risk score; these are the first two digits of the NS metric.
- 5) The total number of active opioid prescriptions is appended to the two-digit composite risk score, to form the final three-digit NS metric.

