## **2.2 DEFINITION OF ASSESSMENTS**

### **2.2.1 NS METRIC**

Appriss Health has developed the NS metric, which uses PDMP data on prescription opioid and benzodiazepine use and aberrant drug behavior (e.g., multiple providers, pharmacies) to compute a score quantifying the extent of the patient's risk in relation to all prescription opioid users. The NS metric is a continuous indicator on a 000-999 scale, with the last digit representing active number of opioid prescriptions (those with  $\geq 9$  prescriptions coded as 9) and the first two numbers representing a composite risk score. Higher scores indicate increased risk for adverse opioid-related outcomes (e.g., overdose). See CTN-0093 Protocol Study Assessments section for details on score composition.

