The study will be powered to the least prevalent but most severe condition among potential patients. Based on the allocation ratio of the national rate of prescription opioid use disorder (POUD) among those prescribed opioid medications in the last year, the prevalence of Poud is 2.1%. A sample of approximately 1,523 (32 positive group) achieves 97.68% power to detect a difference of 0.2 between the area under the ROC curve (AUC) under the null hypothesis of 0.5 and the alternative hypothesis of 0.7 using a two-sided z-test at a significance level of 0.050.

The Completer Population (both training and testing set) will be used to assess the overall discrimination ability of NS metric.

*To determine cut-point threshold values for NS total score:*

The objective is to select the optimal cut-points threshold for NS metric to define low, moderate and high risk groups. We will use a hybrid framework where we can make use of the data driven methods to support the clinician's final decision making. Only the training data set will be used in this portion of analysis.

In the first step, the solution space (a subset of optimum choices of cut-point threshold values) will be identified with the following grid search approach: for each pair of risk groups, for example, low risk vs moderate risk, calculate the following performance measurements for each possible cut-point threshold value:

- Sensitivity (SE)

$$SE = \frac{\text{True Positive Rate}}{\text{True Positive Rate} + \text{False Negative Rate}}$$

- Specificity (SP)

$$SP = \frac{\text{True Negative Rate}}{\text{True Negative Rate} + \text{False Positive Rate}}$$

- Positive Predictive Value (PPV): probability that the risk level is present (based on WHO ASSIST) when the result with NS metric is positive.
- Negative Predictive Value (NPV): probability that the risk level is not present (based on WHO ASSIST) when the test result with NS metric is negative.
- Youden's index:

$$\text{Youden's Index} = SE + SP - 1$$

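### Exploratory Aim 3 compares NS with a version that lacks only a tie-breaking digit, so the size of the difference does not measure how informative the prescription count is

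*SAP*

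**What the plan says.** Protocol 7.2.1 builds the score in steps and ends: "The total number of active opioid prescriptions is appended to the two-digit composite risk score, to form the final three-digit NS metric". SAP 2.2.1 repeats this, "with the last digit representing active number of opioid prescriptions", with nine or more coded as 9.

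SAP 3.5, Exploratory Statistical Aim 3, sets out to "test if the third digit of NS metric (number of opioid prescription) is informative". It defines NS metric v2, "which consists of only the first two numbers of original NS metric, which ranges 00-99", and plans three things:

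- A rank correlation: "correlation between NS metric and NS metric v2 will be examined with Spearman Correlation Coefficients".
- A repeat of the training/validation analyses with v2, to compare its discrimination with that of NS. The stated reading is directional: "We expect the predictive power of NS metric v2 is lower than that of NS metric, which implies the 3rd digit" is predictive.
- A stratified rerun: "We will also repeat the training/validation analysis within each subgroup of patients with same numbers of opioid prescriptions". Average misclassification across these groups is compared with the primary result, and comparable accuracy is taken to show that the third digit represents the count well.

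The aim gives no paired test, interval or margin for NS versus v2, and enters the count as a separate predictor nowhere. The ordinal regression in Aim 2 has NS as a covariate, with sex, pain, general health, depression and substance use history, but not the count as its own term.

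**The concern.** Whether the count carries information about opioid risk is a question about an association with WHO ASSIST, given the composite. The planned contrasts answer something narrower: how much is gained by using the count to order patients who already have the same composite. If few patients share a composite value, that gain is small however predictive the count is. The planned outputs would then not tell a reader how much the count adds. This is the only aim that examines how the NS metric is defined, so the question would remain open although the data to answer it are in hand.

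**Working it through.** **The plan's own figure.** Aim 3 states none. The nearest is in SAP 3.5: "A sample of approximately 1,523 (32 positive group) achieves 97.68% power to detect a difference of 0.2" in AUC (0.7 against 0.5, two-sided 0.05). With m = 32 cases, 1,523 − 32 = 1,491 controls, R = 1,491/32 = 46.6, and a binormal model with equal variances:

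Var(A) = {f²(1 + 1/R + a²/2) + g²(1 + R)/(2R)}/m, where a = √2·Φ⁻¹(A), f = exp(−a²/4)/√(4π), g = −fa/2.

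The standard errors are 0.0504 at A = 0.5 and 0.0508 at A = 0.7. Power = Φ[(0.2 − 1.96 × 0.0504)/0.0508] = Φ(1.99) = 97.68%. The figure reproduces, but it concerns NS against chance, not NS against v2.

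**Step 1: ordering (from the documents alone).** Write NS = 10C + D, with composite C from 0 to 99 and count digit D from 0 to 9. If C₁ ≥ C₂ + 1, then NS₁ − NS₂ ≥ 10 − 9 = 1. No count can reverse two patients whose composites differ.

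**Step 2: ceiling on the AUC difference.** AUC = P(case scores above control) + ½P(tie). Pairs with different composites contribute equally to both AUCs. A tied pair contributes ½ under v2 and 0, ½ or 1 under NS. So |AUC(NS) − AUC(v2)| ≤ T/2, where T is the share of case-control pairs with equal composites. A shift of 0.05 needs T of at least 10%.

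The documents do not give the composite's distribution. If it is roughly normal, T ≈ 1/(2√π × SD):

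| Assumed SD | T | Ceiling T/2 |
|---|---|---|
| 10 | 2.8% | 0.014 |
| 15 | 1.9% | 0.009 |
| 20 | 1.4% | 0.007 |

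**Step 3: simulation.** The first three rows assume a rounded normal composite (mean 40, SD 10 to 20), a count with latent correlation 0.3 with the composite (0.3 or 0.7 in row 3), a modest composite effect and 2.1% high risk. The last two assume a beta(2,3) composite with 40% of patients moved to one value, an independent Poisson(1.2) count and 17.1% moderate/high risk. Both prevalences are the SAP's.

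| Setting | Spearman NS, v2 | AUC gain, NS over v2 | AUC gain, separate terms over v2 |
|---|---|---|---|
| Poisson(1.5) count, OR 1 | 0.9996–0.9999 | 0 | 0 |
| Poisson(1.5) count, OR 1.65 | 0.9996–0.9999 | 0.002–0.005 | about 0.08 |
| 1 + Poisson(0.5) count, OR 1.65 | at least 0.9995 | 0.001–0.003 | about 0.03 (correlation 0.3), 0.015–0.02 (0.7) |
| 40% heaped, OR 2 | 0.969 | 0.025 (ceiling 0.061) | 0.113 |
| 40% heaped, OR 3 | 0.969 | 0.039 (ceiling 0.065) | 0.204 |

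In the second row the count alone has an AUC of about 0.70, above v2's 0.64, yet NS improves on v2 by at most 0.005. The correlation is the same whether the count is useless or predictive.

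**Step 4: the within-count rerun.** With N = 1,523, a beta(2,3) composite, an independent count and 17.1% moderate/high risk, test-set misclassification was:

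| OR per prescription | v2 within count groups | NS, primary analysis |
|---|---|---|
| 1 | 0.392 | 0.395 |
| 2 | 0.395 | 0.404 |
| 3 | 0.394 | 0.413 |

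The largest gap is 0.413 − 0.394 = 0.019. With no margin stated, all three rows could be called comparable, including the one where the count has no effect.

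**Step 5: the alternative.** A likelihood-ratio test of the count added to the composite (same setting as step 4, 300 replicates) rejected in 5.7% of runs at OR 1, 95% at OR 1.25 and 100% at OR 2. The mean in-sample AUC gain was 0.017 at OR 1.25 and 0.114 at OR 2, against 0.0009 and 0.0026 for NS over v2.

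**The case against.** Aim 3 is titled as a validation of the score's definition. Whether the digit, in its existing position, adds discrimination is a fair question, and NS versus v2 answers it. That stands, and it is why the comparison should be kept as description.

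A small gain can still be detected. A paired AUC test of NS against v2 had 84–85% power at OR 1.65 with the 2.1% outcome (about 40% at OR 1.35), and 99–100% with the 17.1% outcome. A reader might therefore infer too much in saying that no paired test could help: it could show that the gain is not zero. It could not show how much the count adds, and the SAP specifies no such test.

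A reader might also infer that no planned output could reveal a predictive count. The documents do not support that. If the rerun yields confusion matrices by count, the trend may be visible: in one simulated case (OR 1.65, composite SD 10) moderate/high prevalence rose through 7%, 12%, 19%, 30% and 43% for counts 0 to 4. That trend is not adjusted for the composite, and average misclassification is the only summary that Aim 3 names for the rerun. The groups are also small: with Poisson(1.5) counts, none holds more than about 8 high-risk patients before the split.

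A third tempting reading is that the aim would lead to the digit being dropped. The SAP has no rule for that. Its reading is directional, and NS exceeded v2 on AUC in every simulated trial at OR 1.65.

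Finally, the distributions are assumed. Every participant has been dispensed an opioid, so a Poisson(1.5) count, with 22% at zero, may be unrealistic, and the composite already reflects dose, overlapping days and prescribers. Less favourable assumptions shrink the separate-terms gain to about 0.02, as in row 3 of the simulation table, but do not close the gap.

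**Conclusion.** The concern holds. That the digit only breaks ties follows from Protocol 7.2.1 and needs no assumption, as does the ceiling of half the tie share. It follows that the Spearman correlation is not evidence about the count, and that the size of the NS-v2 difference does not measure the count's value.

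The magnitudes do rest on assumptions. With composite SD 10 to 20, OR 1.65 and 2.1% high risk, the gain is about 0.001 to 0.005, against about 0.02 to 0.08 with separate terms. The ceilings of 0.007 to 0.014 apply only to smoothly spread composites. Heavy heaping raised the NS gain to about 0.04 at most in the settings tried, still well below the separate-terms gain there. The within-count rerun does not resolve the question through its named summary.

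This is an exploratory aim. No primary aim, cut-point or sample size depends on it, so priority is low to moderate.

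**What to change.** In Exploratory Aim 3:

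- In all completers, fit an ordinal logistic regression of WHO ASSIST level on the two-digit composite and the count as separate terms. Both can be read from the delivered score as its first two digits and its third.
- Test the count by likelihood ratio. Report its odds ratio, and the AUC gain of the two-term model over the composite alone with a bootstrap confidence interval. Refit the model in each bootstrap sample, since the in-sample gain is slightly optimistic (0.0014 on average when the count had no effect).
- Drop the NS-v2 Spearman correlation as evidence. Keep NS versus v2, with a paired confidence interval for the AUC difference, only as a description of what the appended digit adds to the existing score.
- Remove the statement that comparable within-count accuracy shows the count to be well represented. Present any per-count tables as descriptive and unadjusted.

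The cost is one more exploratory model and a few sentences of SAP text. No new data are needed.
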